Title: Innovative Teaching Solutions to Improve the Outcomes of Home Caregivers

V1.01.2023

PI00868

Abstract

Justification. Caring multipathological and polymedicated patients at homes is inexorably growing in OCDE countries, with a greater risk of suffering diverse errors made by their carers. **Objective.** To promote the training of home caregivers using five different educational solutions compared against the natural intervention. **Method.** Prospective, parallel and mixed research study with two phases. *Candidates:* will be home-based caregivers caring either a person with multiple co-morbid conditions or polymedication or a person that have a permanent device implanted such as a Port-a-Cath. *First phase:* Expert groups joined together to design and plan potential educational solutions directed to caregivers based on the identification of medication and home care errors, their causes and consequences and risk factors that favor them. *Second phase:* Inter- and intrasubject single-factor experimental design (6 groups, 5 experimental groups and control, with pre-post- intervention and follow up measures), simple random assignment, to determine the effectiveness several educational solutions (n=420 participants). The study will be carried out in primary care centers and caregivers' associations in Valencian Community, Andalusia, Madrid, Murcia and Catalonia. **Expected results.** To identify critical elements for risk management in the home for caregivers. To find the most effective and optimal educational solution that also reduces the impact of gender bias in this activity.

ClinicalTrial xxxxxxxxx

Overview and aim

The increase in the number of people with chronic diseases is a significant burden of care and consumption of health care resources all over the world. Most are elderly and, in some degree, dependent for their daily activities of a caregiver. Thanks to the work of people caring people at home, these people survive while preserving their well-being as much as possible. This work covers a range of activities from physical and emotional support for the promotion of autonomy to the management of their pharmacological treatment, in many cases applying more complex care. The sex bias generally prompts that the provision of care for dependent persons is carried out by women, which widens the already existing gender gap to the detriment of women.

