The project seeks to put people at the center of interventions while respecting their digital rights. The comparison between 360V, VR, RA, web-based information, written information and standard procedure, to determine which is the best way to train home caregivers in order to increase their technical competences and soft skills, including self-confidence, is the outcome this project would analyze. This study aims to explore the

experience and needs of caregivers (skilled and unskilled) of dependent and chronically ill patients and then to design and test the effectiveness of several interventions aimed at promoting safer medication use in the home.

Methods

Intervention design

This is a prospective, parallel, fully randomized (with simple random assignment of participants to one of six arms) experimental study to compare (inter-group and intra-subject PRE and POST measures) educational interventions aimed at training caregivers using typical scenarios during their work at home in order to reduce medication and caring errors and improve caregivers' motivations and self-efficacy.

Present protocol underwent the revision and approval of an Ethics Committee Board, obtaining the approval in December 2021 and January 2023 (CODES 21/063; 22/079 and 22/080). ClinicalTrial xxxxxxxx

Recruitment

Recruitment will be carried out in the collaborating centers through the programmes for complex chronic patients, schools for carers, and associations and foundations for carers and/or diseases causing dependency situations using the "snowball" technique.

Participants (caregivers) will be recruited during a regular consultation where they go to accompany the person they care for to the consultation, or in a clinical consultation of their own where they can comment that they are caring for a person at home. Recruitment will be carried out through systematic sampling according to the list of people seen in the consultation, using $k=3$. The collaborator will systematically select 1 out of every 3 patients cited in the consultation list. If the person refuses to be included in the study, the next person on the list will be invited and then $k=3$ will be applied.

Additionally, in the recruitment of caregivers, two aspects must be considered:

- Qualification of the caregivers

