- Carers with problems of vertigo, tinnitus, motion sickness, epilepsy, seizures or similar symptoms, severe cardiac conditions or wearing a cardiac pacemaker or hearing aid.

Inclusion criteria for professionals

- Professionals with at least 5 years of experience working in hospitals, health centers and day-care centers.

Intervention design

Medication errors refer to any avoidable incident that may cause inappropriate use of medication, or harm to the patient, while the drug is under the control of the healthcare professional, patient, or caregivers. Care errors to describe any avoidable incident during care, grooming, mobilization that can cause or does cause harm to the patient and that, in our case, occurs in the home and is performed by caregivers.

Care can come from qualified or mostly unqualified people (family members or untrained carers) who take on complex tasks with little training. In this project we consider the limit of 20 hours of training to differentiate between qualified and unqualified carers.

The study includes two phases, a first phase of data collection and a second experimental phase. Some of the centers may not participate in one of these arms due to their idiosyncrasies. The same applies to the day-to-day situations listed in the document.

Phase 1. In this phase, already completed, information on knowledge, needs and differences in responsibility for the safe use of medication and dispensing of care among caregivers has been captured through nominal groups and an online survey disseminated via email to caregiver associations, which has allowed for the identification of errors, causes and consequences and risk factors that favor these errors. This information feeds into the design of situations for the experimental phase.

[figure not shown]
Phase 2. A true experimental design will be conducted to determine the effectiveness of different interventions, each of them reflected in an arm, to reduce errors during the care and administration of medication at home by caregivers.

To be able to determine which educational solutions are optimal, the study has the following arms:

- *Arm 1-Control group:* Natural intervention (actual provision of information and answering of questions). **This arm will evaluate the natural learning during the action.**

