- *Arm 2-Experimental group 2:* Intervention with written materials and demonstration videos specifically designed for this study. **This arm will evaluate the effect of a traditional, more passive form of learning, with little degree of interaction with the content.**
- *Arm 3-Experimental group 3:* Psychoeducational intervention specifically designed for this study. **With this specific intervention, participants will learn by sharing information with the session facilitator and other participants, which will facilitate a more active form of learning, with a higher degree of interaction than the previous arm.**
- *Arm 4-Experimental group 4:* Intervention using immersion 360 degrees specifically designed for this study. **Participants enrolled in this arm, by completing it, is assumed that will experience a form of learning more participatory and immersive than conventional videos, as they can interact with the content by changing the camera angle.**
- *Arm 5-Experimental group 5:* Virtual Reality intervention specifically designed for this study. **Using VR to learn procedures will encourage caregivers to learn in a fully immersive and participatory environment where they will have to interact with the virtual content, enhancing their learning experience.**
- *Arm 6-Experimental group 6:* Augmented Reality Intervention specifically designed for this study. **This intervention will increase participants' skills through active learning as they interact with real-world care situations while receiving simultaneous support from AR devices.**

In each of the experimental groups, key patient care situations will be developed and the educational solutions for each of the arms will be adapted.

The process of this phase of the study is summarized in the following **figure**.

The evaluation of the effectiveness of each of the arms will be measured, among other ways, by recording two attempts to execute the care situation to be trained in the intervention. This recording will be made at three different times: at the baseline visit (pre-intervention), after the intervention (post-intervention) and 6 months after the end of the intervention (follow-up). The control group is an exception, as there is no specific intervention and therefore the post-intervention recording is omitted. Thus, in the case of the control group, only the pre-intervention and 6 months after the intervention will be recorded.

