These recordings will be assessed by means of an objective checklist (rubric), which assesses the errors and learning on which the educational solutions have an impact. This task will be carried out by members of the research team.

Chronological development of the project

Screening visit:

Caregivers will be informed about the study, what their commitment is, what is needed from them and the requirements. Those who are interested and meet the inclusion and exclusion criteria (described in the section Inclusion/exclusion criteria and recruitment), will be asked to sign the consent form.

Subsequently, the centers will randomly assign participants to one of the study arms and construct the registration code for each caregiver, following the guidelines in the recruitment section (the caregiver's date of birth is required).

Start-up visit (Pre-intervention):

At this point, the carers will go to the medical centre to which they belong, where they will be recorded carrying out their simulated carer's work. The recording will be made using a device consisting of neutral glasses or a headband with a small camera to record comfortably. At the beginning of the recording, the caregiver's identification code must be shown. In the same session, at the end of the recording, the centres will explain to the participants that they must fill in a questionnaire with their data, the Pre-intervention Carer's Notebook, which can be accessed from a QR code/link that will be given to them at that moment.

Subsequently, the videos of the start-up sessions of each participant will be recorded and assessed by the research team with the help of staff from the centres following the rubric provided.

Intervention:

- *Intervention application (different sessions according to arm, arms 2 to 6 only).*

At this point, the corresponding intervention will be carried out for each participant. Depending on the arm to which he/she has been assigned, the procedure and duration of the intervention sessions will be different. The information for each intervention is explained in the following sections. It will follow the following scheme:

- *Arm 1 (Control group):* no specific intervention different from the natural one is performed so it will not be necessary to convene the participants of this group for this session.

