- *Arms with intervention at home (Arm 2 - Intervention with written materials and videos, Arm 4 - Intervention with 360° materials and Arm 6 - Intervention with augmented reality):* the intervention is carried out by the caregiver alone at home, so it is useful to hold a training session at the centre to explain to the caregiver the task to be carried out at home.
- *Arms with intervention at the centre (Arm 3 - psychoeducational intervention, Arm 5 - intervention with virtual reality):* the stipulated sessions of each arm will be carried out in the rooms provided in the centres.

Post-intervention visit

Once each arm's own intervention has been received, participants will be called to participate in a new recording of the care work in the medical centre. As in the pre-intervention, at the beginning of the recording, the caregiver's identification code must be shown. At the end, a new link and QR with the Post-intervention Caregiver's Notebook will be shared with them so that they can fill it in online through the link. This flow will be for all arms except for the control arm (Arm 1), where no recording will be carried out and no post-intervention caregiver's notebook will be completed.

Again, the videos resulting from the recordings of this session should be analysed following the available rubric.

Follow-up visit (+6 months)

After 6 months (follow-up phase), participants will be recorded making two attempts at the care they were trained in. As in the previous recordings, at the beginning of the recording, the caregiver's identification code must be shown. At the end, they will be given a new QR and link to the Caregiver's Notebook Follow-up.

Gold Standard (professional group)

In addition to the participants in the control and experimental groups, the study will also include a group of 10 healthcare professionals, who will act as the Gold Standard group. This group will be recorded performing all the care situations to be trained to have a standard measure with which to compare the performance of the caregivers, once they have received the training.

Data analysis

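### Control has no POST measure, so POST comparisons exist only among arms 2 to 6; the plan should name the PRE-adjusted +6-month score as the comparison with control

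*Combined protocol and SAP*

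**What the plan says.** The Abstract sets out the design as "6 groups, 5 experimental groups and control, with pre-post- intervention and follow up measures". The first Intervention design section, under Methods, assigns "participants to one of six arms) experimental study to compare (inter-group and intra-subject PRE and POST measures) educational interventions". Neither makes an exception for control.

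The second Intervention design section (Phase 2) does: "The control group is an exception, as there is no specific intervention and therefore the post-intervention recording is omitted". It adds that "in the case of the control group, only the pre-intervention and 6 months after the intervention will be recorded". Under Chronological development of the project, the Post-intervention visit section repeats the exception and extends it to the questionnaire: "where no recording will be carried out and no post-intervention caregiver's notebook will be completed". Both the rubric score and the notebook measures are therefore absent for control at POST.

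On timing, Phase 2 counts the follow-up recording six months from the end of training. The Intervention section says of control that "it will not be necessary to convene the participants of this group for this session", and of the arms generally that "the procedure and duration of the intervention sessions will be different". No lengths are given.

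The Data analysis section takes differences across PRE, POST and follow-up as outcome variables. They are to be compared by ANOVA or Kruskal-Wallis and explored with a linear mixed model. The section does not say which arms enter which comparison, does not identify the comparison with control, and specifies no adjustment for the PRE score.

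**The concern.** The stated objective is to compare five educational solutions with the natural intervention. A reader of the Abstract, Methods and Data analysis would expect a PRE-to-POST contrast with control, and the visit schedule cannot supply one.

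Two misreadings are then possible when results are reported. The first is that a PRE-to-POST gain in a trained arm is presented as an effect against control, although practice at the recorded task alone could raise the score by an unknown amount. The second is that the mixed model, if time is given a functional form, produces a control value at POST that looks like an estimate but comes from the assumed form. The Data analysis section also makes offering training to control depend on success, without saying which comparison decides it.

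**Working it through.** The only design figure in the plan is a total of 420. It is stated without power, effect size, SD or dropout, so it cannot be reproduced. The check below does not depend on it, except to illustrate standard errors.

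**1. Which contrasts exist.** Six arms by three visits give 6 × 3 = 18 cells. Control at POST is empty, so 17 are observed. With visits treated as categories, a cell-means model has 18 parameters and rank 17. There are 6 × 5 / 2 = 15 arm pairs, of which 5 involve control and 10 do not.

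| Change contrast | Against control | Among arms 2 to 6 |
|---|---|---|
| PRE to POST | 0 of 5 | 10 of 10 |
| POST to follow-up | 0 of 5 | 10 of 10 |
| PRE to follow-up | 5 of 5 | 10 of 10 |

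In total 5 + 30 = 35 of 45 are identifiable. Same-visit contrasts with control number 5 of 5 at PRE, 0 of 5 at POST and 5 of 5 at follow-up.

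**2. What a model-supplied control value at POST would mean.** Let L be the intervention length in weeks (assumed) and take 6 months as 26 weeks. A straight line for control puts POST at a fraction L/(L + 26) of its PRE-to-follow-up change. For L = 1, 4, 8 and 12 this is 1/27 = 0.037, 4/30 = 0.133, 8/34 = 0.235 and 12/38 = 0.316. Assuming no change until after POST gives 0, and assuming all change by POST gives 1. Nothing observed in control separates these.

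**3. Test exposure at follow-up.** Each recording holds two attempts (Phase 2). Arms 2 to 6 arrive with 2 × 2 = 4 earlier recorded attempts and control with 2. The +6-month contrast therefore estimates training plus one extra test session. The size of any retest effect is unknown.

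**4. PRE-adjusted score or change score at +6 months.** With equal PRE and follow-up variances, PRE-to-follow-up correlation r and n per arm, the variance of a control contrast in SD units is 4(1 − r)/n for the change score and 2(1 − r²)/n for the PRE-adjusted score. The ratio is (1 + r)/2. The values of r are assumed, and n = 420/6 = 70 assumes equal arms, all evaluable.

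| r | Variance ratio | SE, change | SE, adjusted |
|---|---|---|---|
| 0.3 | 0.65 | 0.200 | 0.161 |
| 0.5 | 0.75 | 0.169 | 0.146 |
| 0.7 | 0.85 | 0.131 | 0.121 |

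A simulation of 4,000 trials at r = 0.5 gave 0.168 and 0.145.

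**5. Timing (moderate confidence).** If control's 26 weeks were counted from PRE, while arms 2 to 6 count from the end of training, the trained arms would be seen at 26 + L weeks from PRE. For assumed L = 1, 4, 8 and 12 this is 27, 30, 34 and 38 weeks, or 3.8%, 15.4%, 30.8% and 46.2% longer than control.

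**The case against.** **The omission is a declared design choice.** This stands. Phase 2 calls it an exception and gives the reason, and the Abstract and Methods lines are short summaries. A reader might infer that control's POST visit was overlooked; the documents show that it was not. The remaining point is that the summaries and the analysis section were not aligned with the choice.

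**The analysis section already includes follow-up.** This also stands. PRE-to-follow-up differences are among its outcomes and exist in all six arms. The section also refers to the experimental sessions, which only arms 2 to 6 attend, so it can be read as claiming no control value at POST. The fair criticism is that it does not single out +6 months as the comparison with control.

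**The change score would be valid too.** Correct. Adjustment for PRE is preferred for precision and not because a cell is empty. The size of the gain rests on an assumed r and equal variances.

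**The counts do not measure bias.** True. They show what can be estimated. The documents allow no estimate of how much practice or a few weeks' offset would move the score.

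**The timing gap may be closed elsewhere.** Possibly. A figure and the arm-specific sections are not supplied, and the time 0 label in Data analysis may attach to POST alone or to PRE as well. A reader might conclude that control's follow-up is definitely undated; the supplied text does not support that much.

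**A control recording at a POST-equivalent time would be the full remedy.** It would give the immediate effect and equalise test exposure. It would also need extra visits and add a test to an arm of which the plan says "This arm will evaluate the natural learning during the action". That is a trade-off for the sponsor and is not required here.

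**Conclusion.** The point holds as one of specification that should be fixed. No POST, PRE-to-POST or POST-to-follow-up contrast with control can be estimated from data (0 of 5 each). PRE-to-POST gains can be compared only among arms 2 to 6. The single randomised post-baseline comparison with control is at +6 months (5 of 5), and the plan does not identify it as such. These counts follow from the visit schedule alone and confidence in them is high.

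A reader might go further and conclude that the trial has no valid comparison with control, or that the mixed model cannot be fitted. Neither follows. The +6-month comparison survives in all six arms, comparisons among arms 2 to 6 are untouched, and a mixed model can be fitted with the empty cell provided that no control value at POST is taken from it.

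The precision advantage of the PRE-adjusted score (variance lower by 35%, 25% or 15% at r = 0.3, 0.5 or 0.7) depends on the assumed r and on equal variances. The timing point is secondary and held with moderate confidence. Its figures rest on assumed intervention lengths of 1 to 12 weeks.

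**What to change.** 1. Amend the Abstract, Methods and Data analysis to state that POST and PRE-to-POST comparisons are among arms 2 to 6 only; that the comparison with control is the +6-month score adjusted for the PRE score, across all six arms; and that no control value at POST is derived from the mixed model.
2. State as a limitation that arms 2 to 6 reach follow-up with four earlier recorded attempts and control with two, so the contrast includes one extra test session.
3. Unless it is set out elsewhere in the full protocol, define control's time origin for follow-up, align its time since PRE with arms 2 to 6 as far as practicable, and report days from PRE to follow-up by arm. Because durations differ by arm, no single date matches all five. For example, with assumed lengths of 1 to 12 weeks, adding the 6.5-week midpoint to control's schedule caps the mismatch at 5.5 weeks, but it raises the 1-week arm's mismatch from 1 to 5.5 weeks and worsens it for any arm shorter than 6.5/2 = 3.25 weeks. No particular rule is therefore prescribed.

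The cost is low. Items 1 and 2 are text and use PRE and follow-up scores already collected in every arm. Item 3 may move the date of one existing control visit. No visits, recordings or notebooks are added. The change does not recover the immediate effect against control.

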Time of use will be recorded and correlation analyses will be performed to determine the size and direction of the effect on the outcomes. The difference between the measures considered above rated will be considered before and after (PRE and POST intervention (time 0) and FOLLOW UP (+6 months)) the experimental intervention sessions as outcome variables. The distribution of the data will be tested using the Kolmogorov-Smirnov test, the measures will be compared with an ANOVA test for normally distributed continuous variables, and the Kruskal-Wallis test if the distribution is not normal. Given the number of time-ordered and repeated variables per subject, they will be explored using a linear mixed effects model (LMM). Data will be stratified taking into account gender, age, recipient profile and time of use. P values <0.05 are considered to indicate statistically significant differences. Statistical analyses will be performed on R and SPSS. If the intervention is successful, the control group will be invited to receive the treatment of the experimental group on the same terms. The results of this project will be prepared for dissemination according to the contents of the "Standards for reporting qualitative research" (SRQR) guidelines for qualitative studies, the Consort checklist for randomized trials, and the CHEERS checklist for economic outcome evaluations.

Discussion sobre utilidad o lo que hacen otros estudios

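### The time-of-use correlation is not held within arm although session duration depends on arm, so it can report arm differences, in either direction, as an effect of use

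*Combined protocol and SAP*

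**What the plan says.** The Data analysis section opens with the dose question: "Time of use will be recorded and correlation analyses will be performed to determine the size and direction of the effect on the outcomes". It names no restriction to a single arm and no adjustment for arm.

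Three other statements bear on how that sentence would be carried out.

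- Chronological development of the project, Intervention: "Depending on the arm to which he/she has been assigned, the procedure and duration of the intervention sessions will be different". Arms 2, 4 and 6 are delivered so that "the intervention is carried out by the caregiver alone at home". For arms 3 and 5, "the stipulated sessions of each arm will be carried out in the rooms provided in the centres".
- The control group has no intervention session: "so it will not be necessary to convene the participants of this group for this session". The post-intervention flow applies to all arms "except for the control arm (Arm 1), where no recording will be carried out".
- Data analysis again: "Data will be stratified taking into account gender, age, recipient profile and time of use". Arm is not in that list. A linear mixed model is named for the repeated measures, but its terms are not given, so it cannot be assumed to take arm out of the time-of-use question.

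**The concern.** Time of use depends partly on the arm to which a carer is randomised, and the trial is run because outcome may depend on arm too. A correlation taken across arms therefore has two components: the association within arms, which is what a dose-response question asks about, and the covariance between arm mean times and arm mean outcomes. The second can be non-zero when extra minutes do nothing. It is positive if the longer interventions happen to work better and negative if the shorter ones do.

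At stake is a secondary conclusion, namely how much training carers should be given. The plan would describe the coefficient as the size and direction of an effect and judge it at p<0.05. A reader could then conclude that more use helps, or that it harms, when the data show only that the programmes differ. The randomised comparison of arms is not affected.

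**Working it through.** The plan gives no figure for this analysis (no correlation, duration, SD or power), so there is nothing to reproduce. The check is whether an across-arm correlation departs from zero when time has no effect within any arm, and by how much.

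**Inputs from the document.** Total n=420 in six arms (Abstract); significance at p<0.05 (Data analysis).

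**Assumptions.** Equal allocation, so 420/6 = 70 per arm; two-sided test; outcome SD 1 within arm; zero within-arm slope; SD of time within arm 20 min; mean times in arms 2-6 of 60, 80, 90, 120, 120 min; arm effects of 0, 0.1, 0.2, 0.4, 0.4 SD.

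**Formula.** With a zero slope within arm,

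r = cov_B(time, effect) / √[(var_B(time) + var_W(time)) × (var_B(effect) + 1)],

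where B is between arms and W within arms. The rejection rate is approximately Φ(atanh(r)·√(N−3) − 1.96) for positive r.

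**Arms 2-6, effects rising with duration (N = 350).**
- Mean time is 94, with deviations −34, −14, −4, 26, 26; var_B = 2720/5 = 544.
- Mean effect is 0.22, with deviations −0.22, −0.12, −0.02, 0.18, 0.18; var_B = 0.128/5 = 0.0256.
- cov_B = (7.48 + 1.68 + 0.08 + 4.68 + 4.68)/5 = 3.72.
- r = 3.72/√(944 × 1.0256) = 0.120.
- Rate: 0.1201 × √347 = 2.24, and Φ(0.28) = 0.61. Simulation gives 62%.

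**Same values, effects in reverse order.** cov_B = −3.48 and r = −0.112. The rate by the same formula on |r| is Φ(0.13) = 0.55. Simulation gives 55-56%.

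**All 120 pairings of these durations with these effects (simulation).** Rates run from about 5% to 62%, with mean about 20% and median about 12-13%. About four in ten pairings stay below 10%. The population r is negative in 52 of 120 (43%).

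**Cases with no artefact.** Equal mean times in arms 2-6 give about 5%. No arm effects give about 5%. Effects exactly uncorrelated with duration give 4.7% (run with durations of 30-150 min).

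**Narrower spread of durations, effects still rising with duration.** 80-100 min gives r = 0.05 and 16%; 85-95 min gives about 8%.

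**Wider spread.** Durations of 30-150 min with effects of 0-0.5 SD give a mean rate of 25% over the 120 pairings and a maximum of 77%.

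**Control scored as zero minutes at follow-up (a further assumption), all five active arms +0.3 SD, N = 420.**
- Equal times of 94 min: cov_B = 94 × 0.3 × 5/36 = 3.92; var_B(time) = 94² × 5/36 = 1227; var_W = 400 × 5/6 = 333; var_B(effect) = 0.09 × 5/36 = 0.0125. So r = 3.92/√(1560 × 1.0125) = 0.099, and the rate is about 52-53%.
- The five differing times above: cov_B is again 3.92, var_B(time) = 1681, r = 3.92/√(2014 × 1.0125) = 0.087, and the rate is about 43%.
- Across the simulations run, the range is 43-54%.

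**With arm removed.** Correlating time and outcome after centring each within arm gives a rejection rate of about 4-6% in every scenario, with mean r about 0.

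**The case against.** The strongest reply is that the plan never says the correlation is pooled. That is correct: it is silent, and the fault is an analysis left open to a misleading reading.

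A reader might infer that a correlation across arms is bound to show arm differences. The documents do not support this. They give no minutes per arm (the Intervention section refers forward to descriptions that are not in the text available) and no arm effects. The 62% is the top of the range and needs effects ordered with duration. Most pairings give far less, and three conditions give no artefact at all.

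A reader might also infer that control enters at zero minutes. Nothing says so. Control has no session and no post-intervention recording, so it cannot be in a PRE-POST correlation at all. It could enter only at follow-up, and only if someone scored an absent intervention as zero.

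The artefact is also small as a correlation: 0.12² is about 1.4% of variance. This stands, but a plan that tests at p<0.05 and reads direction from the sign can still report it as a finding.

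Finally, adjusting for arm does not make time of use randomised. Carers working alone at home may use the material more because they are keener or more able. This too stands, and it is why the result should be described as an association.

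**Conclusion.** The point holds in limited form. The plan attributes an effect to a time-of-use correlation without holding arm fixed, while duration varies with arm. Run across arms, that correlation can be non-zero in either direction when use itself has no effect. Under the assumed durations of 60-120 min and effects of 0-0.4 SD, the false-positive rate lies between about 5% and 62%, averaging about 20%, with |r| up to about 0.12. The figure of 43-54% applies only if control is scored as zero minutes at follow-up and training has a common 0.3 SD effect.

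All these sizes depend on durations, spreads and effects that the documents do not give. What does not depend on them is the mechanism, and the return to about 5% once arm is removed. The change should be made because it is cheap and the reading at risk is advice on training time. The documents do not support a wider inference that the choice of best educational solution is compromised: the plan also has ANOVA or Kruskal-Wallis and a mixed model for comparing the measures, and nowhere says the choice will rest on this correlation.

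**What to change.** In Data analysis:

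- Limit the time-of-use analysis to arms 2 to 6.
- Replace the correlation by a regression of the outcome (POST or follow-up) on time of use, with arm as a factor and the PRE score as covariate.
- Add an arm-by-time term only where time varies enough within the arm. It may not in arms 3 and 5, where sessions are stipulated, and the slope there may be barely estimable.
- Reword the purpose from determining an effect to *describing the within-arm association (exploratory)*, and state that time of use within an arm is not randomised.
- State that the effect of training is taken from the randomised comparison of arms.

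Cost: a few lines of analysis-plan text and a slightly larger model, with no new data or visits. The dose-response result becomes descriptive and less precise. The precision given up comes from the between-arm component, which is the part that can mislead.
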